1. INTRODUCTION

1.1 Background

Fms-like tyrosine kinase-3 (FLT3) mutations are identified in approximately 30% of patients with acute myeloid leukemia (AML) and confer a poor prognosis, with an estimated 5-year overall survival (OS) of approximately 32% (Kottaridis et al 2001). FLT3 is a receptor tyrosine kinase for the cytokine Flt3 ligand (FLT3L) and is expressed on hematopoietic progenitor cells. The FLT3L transduces signals that promote proliferation and survival, and mutations of the FLT3 receptor present as two general types: internal tandem duplications (ITDs) near the receptor juxtamembrane domain, and single amino acid substitutions within the activation loop of the tyrosine kinase domain (TKD) (Levis 2013). While FLT3-TKD mutations do not confer the same poor prognosis as FLT3-ITD mutations, their presence is associated with resistance to chemotherapy (Whitman et al 2001, Takahashi et al 2016).

In both young and old AML patients, approximately 60% will achieve a complete response to standard induction chemotherapy for acute myeloid leukemia (Rowe 2009). While response to initial therapy is comparable among all patients, in those who relapse with a FLT3 mutation, response to re-induction is significantly less compared to non-FLT3 mutated patients, with a complete response (CR) of 22-24% in two analyses (Ravandi et al 2010, Wagner et al 2011). Due to the poorer prognosis of patients with FLT3 mutation-positive AML, allogeneic hematopoietic cell transplant (alloHCT) is indicated in the first CR (CR1) (Pratz et al 2017). In patients who are able to proceed to hematopoietic cell transplantation (HCT), the relapse rate after transplant is higher compared to non-FLT3 mutated patients (Fleischmann et al 2017, Deol et al 2016). Additional therapeutic options are necessary for those who fail to achieve a CR1 or for those whose disease relapses.

Recent Phase III data combining the first-generation FLT3 inhibitor midostaurin with standard induction daunorubicin and cytarabine identified a statistically significant improvement in median OS with the FLT3 inhibitor of 74.7 months (95% confidence interval [CI] 31.5, not reached) compared to placebo with 25.6 months (95% CI 18.6, 42.9) (Stone et al 2017). Midostaurin as well as sunitinib and sorafenib are multi-kinase inhibitors with non-FLT3 targets. Second-generation FLT3 inhibitors, including quizartinib and gilteritinib, are more selective and potent, with a possible reduction in the development of FLT3-TKD mutations that may confer resistance to FLT3 inhibition therapy (Smith et al 2012, Perl et al 2017).

1.2 Quizartinib

Quizartinib is a potent and selective class III fms-like tyrosine kinase 3 (FLT3)-ITD inhibitor under active investigation (Kampa-Schittenhelm et al 2013). A Phase I dose-finding study using quizartinib as monotherapy in refractory AML demonstrated an overall response rate (ORR) of 30% and a median duration of response (DOR) of 13.3 weeks (Cortes et al 2013). All grades of toxicities included nausea (16%), prolonged QT interval (12%), vomiting (11%), and dysgeusia (11%). In a historical control analysis, patients with refractory AML receiving standard salvage therapy or those who relapsed after stem cell transplantation were evaluated. Those receiving quizartinib achieved a CR of 43% compared to 11% in those who did not receive the agent, and a

CONFIDENTIAL

STUDY DRUG: QUIZARTINIB
PROTOCOL DATE: 10 AUGUST 2020

DEVELOPMENT INNOVATIONS STUDY NUMBER: AML 48
VERSION 4.0

statistically significant improvement in OS was identified (Hills et al 2015). In a randomized Phase II study using quizartinib as monotherapy in patients with at least one second-line therapy or after an HCT, ORR was 47% (Schiller et al 2014).

1.3 CPX-351

Other novel therapies for the treatment of AML have demonstrated improved outcomes. CPX-351 is a cytarabine:daunorubicin liposomal complex demonstrated to improve the induction response rate to 66.7%, compared to 51.2% for in patients with previously untreated AML receiving 7+3 (7 days of standard dose cytarabine and 3 days of daunorubicin) (Lancet et al 2014). A Phase III analysis in patients with secondary AML aged 60 - 75 demonstrated a CR of 47.7% with CPX-351 versus 33.3% with standard regimens (Medeiros et al 2016). In addition, a significant improvement in OS was seen in a subset of patients who proceeded to HCT (Lancet et al 2016a).

CPX-351 was also evaluated in patients who failed to respond to 7+3 induction. Four out of 10 patients who received CPX-351 alone achieved a morphologic CR (Lancet et al 2010). The explanation may be that intracellular 5:1 drug concentration of cytarabine:daunorubicin with cytarabine achieves a half-life of 31.1 hours and daunorubicin 21.9 hours. Compared to standard dosing of free-drug, the half-life of cytarabine and daunorubicin was 13 hours (Lim et al 2010, Tardi et al 2009, Fathi et al 2013, Feldman et al 2011). CPX-351 alone compared to investigator's choice for re-induction in refractory AML achieved a morphologic CR rate of 49.4% compared to 40.9%, although this did not meet a pre-defined statistically significant benefit for 1 year OS (Cohen 2007, Cortes et al 2015). However, a sub-group analysis demonstrated that poor-risk European Prognostic Index (EPI) patients receiving CPX-351 had a statistically significant improvement in OS compared to poor-risk EPI patients receiving standard re-induction therapies (Cortes et al 2015). Patients with FLT3 mutations are not factored into the EPI risk stratification, although associated patient characteristics in those with FLT3-ITD AML, including time of recurrence and non-favorable cytogenetics, could place this patient population into poor-risk EPI, suggesting a benefit with CPX-351 (Breems et al 2005).

The poor prognosis in patients with FLT3 mutation-positive AML who have relapsed or failed to respond to induction therapy is an unmet medical need that warrants investigation with novel therapeutic combinations.

1.4 Rationale for the Study

The purpose of this study is to assess the safety, tolerability, and efficacy of the combination of CPX-351 and quizartinib. The ability to deliver a stable liposomal formulation of cytarabine:daunorubicin packaged at a 5:1 molar ratio combined with continuous potent FLT3 inhibition is hypothesized to potentially provide disease control. A recent pre-clinical study demonstrated synergistic activity when CPX-351 was dosed with an FLT3 inhibitor. This synergy was demonstrated when the FLT3 inhibitor was administered after CPX-351, but not when the FLT3 inhibitor was administered simultaneously or prior to CPX-351 (Edwards et al 2017). Investigation of this novel combination in the relapsed/refractory population is reasonable in this high-risk disease population. Since OS in AML is directly related to achieving

CONFIDENTIAL

STUDY DRUG: QUIZARTINIB
PROTOCOL DATE: 10 AUGUST 2020

DEVELOPMENT INNOVATIONS STUDY NUMBER: AML 48
VERSION 4.0

disease control (a molecular CR), the goal of this study is to determine if novel cytoreduction with CPX-351 combined with targeted FLT3 inhibition can achieve improved disease control over what has been previously reported in the literature.

Patients with relapsed or refractory FLT3 mutation-positive AML have limited options. A goal of this treatment is to achieve adequate disease control that may potentially allow a bridge to consolidative cellular therapeutic intervention (e.g., HCT or donor lymphocyte infusion [DLI]) for some patients. In patients who are not candidates for or decline a cellular intervention, the treatment goal is to achieve definitive disease control with the combination of CPX-351 and quizartinib followed by quizartinib maintenance.

In all patients with AML who relapse after an alloHCT, those who receive treatment with chemotherapy, DLI, and/or a second alloHCT achieve a CR rate of 29% with a 5-year OS \leq 11% in those who relapse less than 2 years after first transplant and \leq 31% for those who relapse 2 years or more after first transplant (Weisdorf et al 2013). Currently, it is believed that many relapsed FLT3 mutation-positive AML patients would not have received an FLT3 inhibitor as part of a prior regimen. Novel chemotherapy in combination with a targeted FLT3 inhibitor may provide a significant improvement in survival for this patient population compared to the current standard of care.

1.5 Risks and Benefits

The risks associated with the study derive from the novel combination of CPX-351 with quizartinib. The most anticipated side effect is pancytopenia, with potentially prolonged neutropenia and thrombocytopenia compared to standard induction or salvage chemotherapy. In a randomized study in AML patients, CPX-351 demonstrated a median time to absolute neutrophil count (ANC) \geq 1000 of 36 days compared to 32 days with standard cytarabine and daunorubicin (7+3). In addition, there was a statistically significant increase in Grade 3 or Grade 4 infections. However, infection-related mortality has not been demonstrated. In the same study, platelet count recovery to $>$ 100,000 was 37 days compared to 28 days in those receiving 7+3. Quizartinib in combination with cytarabine and daunorubicin was associated with 21% of study participants showing Grade \geq 3 toxicity for both neutropenia and thrombocytopenia. However, there was no prolonged period of pancytopenia, suggesting that the proposed novel combination of CPX-351 and quizartinib may not contribute to a longer period of myelosuppression than what is expected with CPX-351 alone. Grade 3 and higher febrile neutropenia was identified in 63.5% of patients receiving CPX-351 alone (Lancet et al 2014) and in 47% of patients receiving quizartinib alone (Altman et al 2018).

CPX-351 contains daunorubicin, an anthracycline that has a known association with cardiomyopathy at threshold doses of 550 mg/m². Patients will be excluded if their cumulative dose of an anthracycline exceeds this threshold. To date, quizartinib has not been associated with cardiomyopathy or a reduction in the ejection fraction. Quizartinib has been associated with QT prolongation in a dose dependent manner. In study AC220-007 (Quantum-R) in the relapse/refractory FLT3+ AML population, Eight (3.3%) subjects in the quizartinib arm had ECG QTcF values $>$ 500 ms (Grade 3 QTcF) by central ECG reading. (Quizartinib Investigator Brochure 2020. CPX-351 has not been associated with significant QTc prolongation (CPX-351 US package insert [USPI]). For this study, these cardiac risk factors will need to be monitored

CONFIDENTIAL

STUDY DRUG: QUIZARTINIB
PROTOCOL DATE: 10 AUGUST 2020

DEVELOPMENT INNOVATIONS STUDY NUMBER: AML 48
VERSION 4.0

and accounted for independently. Dose modifications for QTcF prolongation will be based upon pre-specified monitoring and criteria (see Section 8).

All grades of gastrointestinal toxicities associated with CPX-351 were similar to standard induction 7+3, with the most frequent being nausea (47%), diarrhea/colitis (45%), mucositis (44%), and constipation (40%). However, Grade 3 and higher gastrointestinal toxicities were less than 10% (Lancet et al 2016b). In Phase I/II investigations, quizartinib was found to be associated with all grades of nausea (16%), vomiting (11%), and diarrhea (18%) (Cortes et al 2013, Schiller et al 2014).

Given that the toxicities identified with each agent have minimal overlap, it is hoped that the novel combination will not result in the potentiation of the toxicity of either agent alone. A potential beneficial effect of this combination may be the protective effect of quizartinib on normal hematopoietic progenitor cells after exposure to chemotherapy. If dosed sequentially following CPX-351, this may attenuate the effects that CPX-351 has on healthy stem cells without compromising the effect on the leukemic cells (Taylor et al 2017). This potential benefit of the novel combination will be measured based on the timing of myeloid count recovery and comparing this data to data from prior CPX-351 studies.

It is assumed that there are four patient groups who may derive benefit on study for relapsed or refractory FLT3 mutation-positive AML. The first group includes patients who have primary refractory FLT3 mutation-positive AML and who fail first-line therapy with routine induction regimens with or without an FLT3 inhibitor. The second group includes patients with FLT3 mutation-positive AML who have relapsed after HCT. In both scenarios, the study intervention will likely act as a bridge to either an HCT or a DLI. The third group includes patients with relapsed FLT3 mutation-positive AML who were excluded from or declined alloHCT. In this patient population, the FLT3 inhibitor would continue as maintenance therapy. The final group of patients includes those who acquire an FLT3 mutation at relapse. This occurs more frequently in patients with epigenetic-modifying gene mutations at diagnosis (IDH1/2, DNMT3A, TET2) (Shih et al 2002, Wakita et al 2013). Depending on the management choice at the initial diagnosis and initial CR, the last clinical scenario may be a bridge to a first or second HCT or to a DLI.

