7.5.2 Precautions and Risks Associated with CPX-351

- Cardiotoxicity

The total cumulative dose of non-liposomal daunorubicin >550 mg/m² has been associated with an increased incidence of drug-induced congestive heart failure. In patients who received radiation therapy, the maximum tolerable lifetime dose is 400 mg/m². Calculate maximum lifetime exposure prior to each cycle as shown in Table 1.

Table 1 Cumulative Exposure of Daunorubicin per Cycle of CPX-351

Therapy	Daunorubicin per Dose	Number of Doses per Cycle	Daunorubicin per Cycle
First induction cycle	44 mg/m ²	3	132 mg/m ²
Second induction cycle	44 mg/m ²	2	88 mg/m ²
Each consolidation cycle	29 mg/m ²	2	58 mg/m ²

CONFIDENTIAL

See dose modification/administration guidelines (Appendix G).

- Hemorrhage

12% Grade ≥ 3 (8% in control/7+3 arm), fatal non-disease associated CNS hemorrhage 2% (0.7% in control arm)

- Hypersensitivity

Known in patients receiving cytarabine and daunorubicin. See dose modification/administration guidelines (Appendix G).

- Tissue necrosis

Administer by central venous catheter

- Embryo-fetal toxicity

Counsel to avoid pregnancy, and to use contraception through 6 months after last administration of agent. Because of the potential for serious adverse reactions in breastfed infants, advise lactating women not to breastfeed during treatment with CPX-351. In males, CPX-351 may cause infertility. In male patients wishing to conceive in the future, cryopreservation of sperm prior to administration is recommended.

- Cytopenias

Prolonged thrombocytopenia (<50 beyond Day 42) 28% (versus 12%) in induction and 25% (versus 16%) in consolidation; prolonged neutropenia (ANC <500 beyond Day 42) 17% (versus 3%) in induction and 10% (versus 3%) in consolidation. See dose modification/administration guidelines (Appendix G).

- Chemistry abnormalities

Hyponatremia (14%, 6% with consolidation), hypokalemia (9%, 6% with consolidation), hypoalbuminemia (7%, 2% with consolidation), hyperbilirubinemia (6%, 2% with consolidation), and elevated ALT (5%, 0% with consolidation); all were similar in comparison to 7+3.

The most common serious adverse reactions (incidence $\geq 5\%$) were dyspnea, myocardial toxicity, sepsis, pneumonia, febrile neutropenia, bacteremia and hemorrhage. Adverse reactions led to discontinuation of CPX-351 in 18% of patients (13% in the control arm).

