9.10 Time to Absolute Neutrophil Count (ANC) and Platelet Count Recovery

Time to neutrophil recovery is defined as the time from each CPX-351 cycle Day 1 to when the peripheral ANC is $\geq 500/\mu\text{L}$. Time to platelet recovery is defined as the time from each CPX-351 cycle to when the peripheral blood platelet count is $> 50,000/\mu\text{L}$. Delayed neutrophil recovery is defined as having an ANC $< 500/\mu\text{L}$ > 56 days from each CPX-351 cycle Day 1. Delayed platelet recovery is defined as having a platelet count $< 50,000$ > 56 days from each CPX-351 cycle Day 1.

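### The planned count-recovery comparison with prior CPX-351 studies does not match the cited CPX-351 figures on threshold or on cut-off day, and each mismatch tilts its own comparison toward the combination

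*Combined protocol and SAP*

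**What the plan says.** **The comparison.** Section 1.5 suggests that quizartinib given after CPX-351 may spare normal progenitor cells, and says this benefit "will be measured based on the timing of myeloid count recovery and comparing this data to data from prior CPX-351 studies". It does not name the studies.

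**The CPX-351 recovery times cited.** Section 1.5 gives a median time to an ANC of at least "1000 of 36 days compared to 32 days with standard cytarabine and daunorubicin (7+3"). Platelet recovery to above "100,000 was 37 days compared to 28 days in those receiving 7+3".

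**The CPX-351 delay rates cited.** Section 7.5.2 reports "prolonged neutropenia (ANC <500 beyond Day 42) 17% (versus 3%) in induction", and 28% versus 12% for platelets below 50 beyond Day 42 of induction.

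**What this trial measures.** Section 9.10: "Time to neutrophil recovery is defined as the time from each CPX-351 cycle Day 1 to when the peripheral ANC is" at least 500/µL. For platelets the clock runs "to when the peripheral blood platelet count is" above 50,000/µL. Delayed recovery means still below those levels more than 56 days after Day 1 of the cycle. Section 2.3.2 uses the same levels and the same 56 days. Section 10.4 promises Kaplan-Meier estimates with 95% confidence intervals for medians.

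**A second definition of delay.** Section 5.2 still defines delayed neutrophil recovery as ANC below 500/µL at Day 42 from the first CPX-351 day, as the trigger for a marrow examination.

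**The concern.** A comparison with historical data is informative only if both sides measure the same thing. Here the recovery endpoint is set at half the count levels behind the cited medians, and the delay endpoint is read 14 days later than the cited rates.

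Both differences have a known sign within a patient. ANC reaches 500 no later than it reaches 1000, and platelets reach 50,000 no later than 100,000. A patient unrecovered at Day 56 was also not durably recovered at Day 42. If populations and treatment effects were identical, the combination would therefore tend to show shorter recovery times and fewer delays than the cited CPX-351 figures. That could be read as support for marrow protection. It would also blur the opposite signal, and Section 1.5 itself names pancytopenia as the side effect most expected.

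**Working it through.** The plan states no calculation for count recovery, so there is no figure of its own to reproduce. The check sets the definitions side by side and then sizes each mismatch under stated assumptions.

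**1. Definitions**

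| Quantity | Cited CPX-351 figure | This trial (2.3.2, 9.10) | Difference |
|---|---|---|---|
| Neutrophil recovery time | ANC ≥1000, median 36 days (1.5) | ANC ≥500 | 500/1000 = 0.5 |
| Platelet recovery time | >100,000, 37 days (1.5) | 50,000 | 50,000/100,000 = 0.5 |
| Delayed neutrophils | ANC <500 beyond Day 42, 17% (7.5.2) | ANC <500 beyond Day 56 | 56 − 42 = 14 days |
| Delayed platelets | <50 beyond Day 42, 28% (7.5.2) | <50,000 beyond Day 56 | 14 days |

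The recovery times differ on threshold only, and the delay rates differ on cut-off only.

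**2. Threshold mismatch (neutrophils)**

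Let d be the lag from ANC 500 to ANC 1000. The documents do not give it; 2, 4 and 7 days are assumed. With no drug effect and the same population, the median to ANC 500 is 36 − d:

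- d = 2: 34 days
- d = 4: 32 days
- d = 7: 29 days

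For scale, the cited gap between CPX-351 and 7+3 is 36 − 32 = 4 days.

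To see how often 30 patients would show a median below 36 days, recovery times were simulated as lognormal with median 36 − d. The spread was set so that 17% exceed Day 42: σ = [ln 42 − ln(36 − d)] / z(0.83), which gives 0.221, 0.285 and 0.388. The matched case used median 36 and an assumed σ of 0.2. The last two columns multiply every recovery time by 1.1 or 1.2 (assumed).

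| Lag | Same population | 10% slower | 20% slower |
|---|---|---|---|
| 0 (matched) | 49% | 2% | <0.1% |
| 2 days | 87% | 22% | 0.5% |
| 4 days | 97% | 64% | 15% |
| 7 days | 99% | 92% | 65% |

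The slowing that exactly cancels the lag is 36/(36 − d) − 1: 36/34 gives 5.9%, 36/32 gives 12.5%, and 36/29 gives 24.1%.

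**3. Cut-off mismatch**

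Suppose the unrecovered share halves every h days after Day 42 (assumed). The share at Day 56 is then the Day 42 share × 2^(−14/h).

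| h (days) | ANC, from 17% | Platelets, from 28% |
|---|---|---|
| 7 | 4.3% | 7.0% |
| 14 | 8.5% | 14.0% |
| 28 | 12.0% | 19.8% |
| 56 | 14.3% | 23.5% |

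These are not outer limits. The lognormal curves of step 2 have a thinner tail and put the ANC share beyond Day 56 at 1.2%, 2.5% and 4.5% for lags of 2, 4 and 7 days.

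**4. Whether the collected counts could repair this afterwards**

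Appendix D schedules no blood count between Day 21 and Day 35 of induction, and none between Day 6 and Day 35 of consolidation. Scheduled visits alone cannot resolve a difference of a few days. Section 5.2.1 does require counts three times a week, but only for patients discharged after a clear Day 21 marrow and for outpatient consolidation.

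**The case against.** Several points stand against reading more into this.

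- **A reader might infer that the combination will look faster even with no drug effect.** The documents do not support that. This trial enrols relapsed or refractory patients, some after transplant. The randomised CPX-351 comparison with 7+3 in Section 1.3 was in previously untreated AML, and Section 1.5 does not describe the population behind its medians. Recovery about 6% to 24% slower would cancel a lag of 2 to 7 days.
- **A reader might infer one comparison with both faults.** No single cited benchmark differs on both threshold and cut-off. A later cut-off lowers a proportion; it does not shorten a Kaplan-Meier median.
- **A reader might infer that nothing in the trial matches a CPX-351 figure.** Section 5.2 defines delayed neutrophil recovery at ANC below 500 and Day 42, the threshold and day behind the 17%. It is a trigger for a marrow examination and not an endpoint, but it exists.
- **A reader might infer that extra myelosuppression would go unseen.** The lead-in stopping rule (Sections 5, 10.1 and 10.5.1) counts delayed recoveries in absolute terms, and adverse events are CTCAE-graded (10.4.3). Neither depends on historical data.
- **The comparison carries no test, margin or decision.** It is a rationale statement, marrow protection is not in the Section 1.6 hypothesis, and the comparator studies are unnamed. They could report recovery at 500 and 50,000.

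These points limit the consequence but do not remove the mismatch. Section 1.5 states how the benefit will be measured, and the only CPX-351 figures it offers are on other definitions. An unknown opposing population difference does not correct a known bias. With no threshold fixed in advance, one could be chosen after the data are seen.

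**Conclusion.** The concern holds in a limited form. The recovery endpoint uses exactly half the count levels behind the cited CPX-351 medians, and the delay endpoint in 9.10 is read 14 days later than the cited CPX-351 rates. Other things equal, each mismatch biases its own comparison toward the combination.

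That direction follows from the definitions alone; the size does not. Under the assumed lags the median shift is 2 to 7 days, set against a cited 4-day difference between CPX-351 and 7+3. Under the assumed halving times the 17% falls to between 4.3% and 14.3%, and the 28% to between 7.0% and 23.5%. The lag, the halving time, the lognormal shape and the slowing factors are all assumptions.

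The net direction in the actual trial is uncertain, because relapsed or refractory patients may recover more slowly. The response-rate test and the stopping rule are unaffected. The correction is still worth making, because it is cheap and the comparison cannot be interpreted without it.

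**What to change.** 1. In 2.3.2 and 9.10, keep the current endpoints and add (a) Kaplan-Meier time to ANC ≥1000/µL and to platelets ≥100,000/µL from Day 1 of each CPX-351 cycle, and (b) the proportions with ANC <500/µL and platelets <50,000/µL beyond Day 42 as well as beyond Day 56.
2. Reconcile the definitions of delayed recovery in 5.2 (Day 42) and 9.10 (Day 56).
3. In 1.5, name the comparator study or studies, limit the comparison to matched thresholds and cut-offs, and call it descriptive because the populations may differ. Matching definitions does not remove that confounding.
4. Enter in the eCRF the interim counts that are drawn: the three-times-weekly counts under 5.2.1 for discharged and outpatient consolidation patients, and any inpatient counts taken in routine care.

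**Cost.** Endpoint wording, a few derived variables and modest extra data entry. The date of ANC above 1000 is already needed to time consolidation and maintenance (5.2.3, 5.2.4), and 9.1 already uses 1000 and 100,000 to define CR. Recovery times will be less precise for patients without frequent counts, and the report should say so.
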